14 STATISTICS

A statistical analysis plan (SAP) will be prepared and finalized prior to data analysis. This document will provide further details regarding the definition of analysis variables and analysis methodology to address all study objectives.

14.1 Analysis Sets

All subjects who have received at least one dose of study medication will be included in the Safety Population. All analyses of safety will be performed for the Safety Population. The Intent-To-Treat (ITT) evaluable population will consist of all subjects in the Safety Population with CEA and IGA (when available) component scores recorded at screening and/or baseline and at least 1 post-baseline visit. The ITT population will be used to assess clinical activity data.

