7.2 Part B Study Design

Subjects will be randomized 2:1 to receive topical administration of BMX-010 or Placebo which will be dosed at the concentration, formulation, and frequency as defined by Part A. Study product will be applied liberally to Acne Vulgaris on the face. The planned treatment duration is a minimum of 7 days and a maximum of 28 days. Completion of 28 days of treatment will be recommended to all subjects; however, subjects who have full clearing of the Acne Vulgaris, as determined by the clinical center investigator, may stop therapy and remain in the study with a final evaluation at Day 29 or Day 43 at the discretion of the investigator. There will be weekly visits with follow-up done at approximately Days 8, 15, 22, 29 and 43.

Figure 7.a Study Design for both parts

Following written informed consent, subjects will undergo screening evaluations within 14 days prior to the first application of study drug. The screening evaluations will include complete medical history, complete physical examination (including vital signs, weight, and height), clinical laboratory evaluations, urine pregnancy test for females of child-bearing potential (a negative pregnancy test is required within 48 hours prior to the start of drug treatment), concurrent medical conditions, and concomitant medication assessments.

Subjects will be scored by the clinician for IGA. The clinician will also obtain counts of the inflammatory and noninflammatory lesions on the face.

The subject will be asked a series of Patient Reported Outcomes (Appendix A).

In **Part A**, all eligible Subjects enrolled will receive the active study drug, BMX-010. Subjects will treat their Acne Vulgaris on the face with the study product. This will be demonstrated at the Baseline visit. Subjects will be instructed by the clinical center staff and informed how often they should dose each day (QD or BID).

In **Part B**, all eligible Subjects enrolled will be randomized to the study drug (BMX-010) or Placebo. Subjects will treat their Acne Vulgaris on the face with the study product. This will be demonstrated at the Baseline visit. Subjects will be instructed by the clinical center staff and informed how often they should dose each day, which will have been confirmed by Part A of the study.

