8.3 Criteria for Discontinuation or Withdrawal of a Subject

All subjects are free to withdraw from study participation at any time, for any reason, and without prejudice to their further medical care. In addition, the investigator may terminate a subject from the study at any time. The primary reason for discontinuation should be recorded on the case report form (CRF) using one of the following categories:

1. Adverse event. The subject experiences an AE that imposes an unacceptable risk to the subject's health, or the subject is unwilling to continue because of an AE.
2. Lack of therapeutic effect. The investigator has determined that study drug administration is not benefitting the subject, and continued participation poses an unacceptable risk to the subject.
3. Inclusion/exclusion criteria violation. The investigator discovers that the subject did not meet all of the inclusion/exclusion criteria after study enrollment.
4. Protocol noncompliance. The subject has a significant protocol deviation, does not comply with study drug administration schedule, or fails to adhere to other study requirements as stated in the protocol.
5. Lost to follow-up. The subject does not return to the clinic for scheduled assessments, and does not respond to the site's attempts to contact the subject.
6. Voluntary withdrawal. The subject wishes to withdraw from the study. The clinical center should attempt to determine the underlying reason for the voluntary withdrawal and document it on the CRF; if the underlying reason is documented as an AE or lack of

efficacy, the category of withdrawal should be marked in the corresponding category and not as voluntary withdrawal.

7. Study termination. The sponsor, Institutional Review Board (IRB), or regulatory agency terminates the study.
8. Pregnancy.
9. Other. Any reason that does not fall into 1 of the above categories. The specific reason should be recorded on the CRF.

Following early discontinuation from the study, the subject will be informed regarding the additional study evaluations that are necessary to monitor his/her safety. These subjects will be encouraged to participate in the final follow up study visit.

In order to meet the number of specified evaluable subjects, a discontinued or withdrawn subject may be replaced and the newly enrolled subject will be assigned the identical treatment of the withdrawn subject.

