9 TREATMENT OF SUBJECTS

9.1 Treatments Administered

9.1.1 Phase 1/Phase 2 Cohorts

Part A

Cream or gel: BMX-010 0.03% or BMX-010 0.1% or Placebo QD
Cream or gel: BMX-010 0.03% or BMX-010 0.1% or Placebo BID

Part B

BMX-010 dose & formulation determined in Part A vs Placebo. QD or BID frequency as determined in Part A will be conducted.

In this study, up to 210 subjects will be enrolled.

In **Part A**, up to 60 subjects will be enrolled. Subjects will not be randomized and treatment concentration, formulation, and dosing frequency will be at the discretion of the clinical center investigator. All subjects will receive study drug at either 0.03% or 0.1% concentration. They will dose either QD or BID as indicated by the clinical center investigator during the baseline and other weekly visits throughout the study.

In **Part B**, up to 150 subjects will be enrolled. This will be a double-blind study, where the investigator and subject both will not know whether study drug or Placebo has been dispensed. Subjects will be randomized to BMX-010 or Placebo (2:1) in accordance with the randomization schedule. The Placebo cream is color-matched to the study drug, the Placebo gel is not. Up to 100 subjects will be randomized to BMX-010 and up to 50 subjects will be randomized to Placebo.

Although acne occurs on the face *and* trunk, efficacy assessment by IGA will be limited to the face as that is the most frequent site of involvement. However, the study product may be applied to all affected areas during this clinical trial.

When subjects apply QD, it can be applied any time of the day. When it is applied BID it should generally be applied 12 hours apart.

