11.1 IGA

The Investigator Global Assessment (IGA) is a five scale (0 to 4) static evaluation of overall Acne Vulgaris severity (as described below). The change in IGA scores from Baseline through the final follow up visit will be assessed as endpoints in the study.

Drug treatment and efficacy assessment by IGA will be limited to the face. For a score of Clear, residual hyperpigmentation and erythema may be present.

Grade	Description
0 = Clear	No papules and/or pustules; no erythema
1 = Minimal	Rare papules and/or pustules; faint, up to but not including mild erythema
2 = Mild	Few papules and/or pustules; mild erythema
3 = Moderate	Pronounced number of papules and/or pustules, but less than numerous papules and/or pustules; moderate erythema
4 = Severe	Numerous papules and/or pustules, occasionally with confluent areas of inflamed lesions; moderate to severe erythema

There is no single, standardized grading system for severity of acne [20].

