14.4 Safety Analysis

All treatment-emergent AEs will be summarized by dose group and indication (AD or PS). Counts and percents will be presented by treatment group for each observed system organ class (SOC) and preferred medical diagnosis.

The preferred terms and SOCs will be summarized in the following set of tables:

- All AEs;
- All AEs by maximum level of intensity;
- All AEs by closest relationship to the study medication.

Laboratory test variables will be summarized by dose group and study visit using descriptive statistics. Laboratory data collected from baseline and up to 7 days after a subject's last dose of study drug (or the date of the final follow up visit) will be included in the analysis.

Descriptive statistics will be used to summarize vital signs by dose group and study visit. Vital sign data collected from baseline and up to 7 days after a subject's last dose of study drug (or the date of the final follow up visit) will be included in the analysis.

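### Section 14.1 ties the only efficacy set, labelled ITT, to a score the trial does not collect, and Section 8.3 lets Part B replacements bypass randomisation

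*Protocol*

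**What the plan says.** **Efficacy set.** Section 14.1 defines a Safety Population (anyone dosed at least once) and, within it, an ITT evaluable population of subjects "with CEA and IGA (when available) component scores recorded at screening and/or baseline and at least 1 post-baseline visit". The next sentence shortens the name and gives the set its purpose: "The ITT population will be used to assess clinical activity data". No other efficacy set is named.

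**What is measured.** Section 11.1 describes the IGA as a "five scale (0 to 4) static evaluation of overall Acne Vulgaris severity". The synopsis (Criteria for Evaluation), Table 4.a and Sections 11 and 12 add patient-reported outcomes and lesion counts. CEA is absent from all of these and from the abbreviations in Section 3.

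**Safety tables.** Section 14.4 has adverse events "summarized by dose group and indication (AD or PS"), although the trial enrols acne only.

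**Replacement.** Section 8.3 opens its rule with the purpose, "In order to meet the number of specified evaluable subjects", and continues: "a discontinued or withdrawn subject may be replaced and the newly enrolled subject will be assigned the identical treatment of the withdrawn subject". It does not distinguish Part A from Part B.

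**Part B assignment.** Section 7.2 says "all eligible Subjects enrolled will be randomized to the study drug (BMX-010) or Placebo". Section 9.1.1 says "Subjects will be randomized to BMX-010 or Placebo (2:1) in accordance with the randomization schedule".

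**The concern.** Part B's first primary objective (Section 6.1) is a randomised, double-blind comparison with placebo. Two rules in the protocol work against it.

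First, the set on which that comparison would be made has an entry condition whose meaning must be guessed, and the set is not what its name promises. An ITT set keeps everyone randomised. This one requires dosing and a post-baseline score, both of which come after randomisation. If loss before the first post-baseline score differs between the arms and is related to outcome, the comparison is biased.

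Second, a Part B subject brought in under Section 8.3 would have a treatment fixed by who withdrew, not by chance. Anyone who knew or had guessed the predecessor's arm would know the newcomer's arm before enrolling that person. Concealed allocation is meant to prevent exactly this.

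**Working it through.** **1. Can membership of the set be determined?** There are two readings of the Section 14.1 condition.

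- The parenthesis applies to the IGA only, so CEA is required. No CEA is collected, so nobody qualifies.
- The parenthesis applies to both scores. A subject is then excused from whatever is unavailable, so almost nobody is excluded.

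The text does not choose between them. The phrase about component scores fits neither, because the IGA in the synopsis and in Section 11.1 is one grade. Together with the AD/PS wording in Section 14.4, this indicates text carried over from a protocol for another indication.

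**2. How much could the placebo comparison be affected?** From the protocol (Section 9.1.1): up to 150 Part B subjects at 2:1, that is 150 × 2/3 = 100 on BMX-010 and 150 × 1/3 = 50 on placebo, as stated there. The protocol gives no loss rate, response rate, alpha or power, so the rest is assumption:

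- response among assessed subjects 30% in both arms;
- response among unassessed subjects r, the same in both arms, between 0 and 30%;
- share unassessed L_A (active) and L_P (placebo).

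The rate over all randomised subjects in an arm is (1 − L) × 0.30 + L × r = 0.30 − L × (0.30 − r). The dosed-and-assessed set shows 0.30 in both arms. Its error against all randomised subjects is therefore

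error = (L_A − L_P) × (0.30 − r).

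| Loss, active v placebo | r = 30% | r = 15% | r = 0 |
|---|---|---|---|
| 5% v 5%, or 10% v 10% | 0 | 0 | 0 |
| 10% v 5% | 0 | 0.05 × 0.15 = +0.75 points | 0.05 × 0.30 = +1.5 points |
| 5% v 10% | 0 | −0.75 points | −1.5 points |
| 15% v 5% | 0 | 0.10 × 0.15 = +1.5 points | 0.10 × 0.30 = +3.0 points |

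The standard error of the difference with 100 and 50 subjects is √(0.3 × 0.7 × (1/100 + 1/50)) = √0.0063 = 0.0794, or 7.9 points. So 1.5 points is 1.5/7.94 = 0.19 standard errors, and 3.0 points is 0.38.

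**3. Can Section 8.3 and the randomisation rule both hold in Part B?** Sections 7.2 and 9.1.1 send every enrolled Part B subject through the 2:1 schedule. Section 8.3 makes replacement optional, but once it is used the treatment is prescribed. A Part B replacement cannot both take the next scheduled assignment and be given a predetermined one. The protocol describes no separate replacement list, and such a list would still not make the replacement randomised.

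**4. Could the predecessor's arm be known or inferred?** The protocol itself shows three routes.

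- The placebo gel is white and does not match the active gel (Sections 9.1.1 and 9.2.6). This applies if the gel is taken into Part B.
- Site staff grade skin discolouration at visits (Section 12.5), and Section 10.2 expects discolouration in more than 30% of subjects.
- Sites hold a key for unblinding (Section 9.1.2).

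**The case against.** The strongest reply is that little depends on this. The trial is exploratory by title, its sample size has no statistical basis (Section 14.6), and Section 14 leaves analysis details to the SAP. Section 14.1 states its rule openly, so the ITT label misleads nobody who reads it. Loss before any score should be rare: the first dose is given in clinic (Section 7.2), subjects stopped for a related Grade 2 or higher event still return for visits (Section 7.2.1), and early discontinuers are encouraged to attend the final visit (Section 8.3). Replacement is optional, sites are blinded, and an inherited arm came originally from the 2:1 schedule.

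Much of this stands, and it is why the bias is called small. It does not remove the point. The protocol does not leave the set to the SAP; it fixes one, in terms that cannot be resolved. Blinding does not fully answer the replacement problem, given the routes listed above. And an arm inherited from someone who withdrew is not a random assignment of the newcomer.

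A reader might infer more than the text supports:

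- *That the efficacy set is certainly empty.* This follows only on the first reading of the parenthesis.
- *That the ceilings of 150 evaluable subjects (synopsis) and 150 enrolled subjects (Section 9.1.1) contradict each other.* Both are upper limits. Enrolling at most 150 satisfies both, and optional replacement can stop there.
- *That the replacement rule also damages Part A.* Part A is open-label and not randomised. There the sentence is at most a narrow exception to investigator choice, with no evident statistical consequence.
- *That selection bias has been shown.* The protocol leaves a way in for it; nothing shows that it would occur.

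**Conclusion.** Three statements hold.

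- Membership of the only efficacy set is undetermined as written.
- The set is not ITT, because randomised Part B subjects who were not dosed or have no post-baseline score leave the placebo comparison.
- The Section 8.3 replacement rule, which is not limited to Part A, contradicts randomisation of every Part B subject.

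The first and third rest on the text alone. The size of the second rests on assumed rates. It is zero when loss is equal in the arms or when unassessed subjects respond like the others. It is at most 1.5 points (about 0.2 standard errors) at 10% v 5% loss, provided unassessed subjects respond no better than the assumed 30%. A wider gap in loss raises it in proportion. No number of replacements can be derived from the protocol. The wording should be corrected, but this does not by itself undermine Part B.

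**What to change.** **Section 14.1.** Delete CEA, the availability parenthesis and the reference to component scores. Define the Part B primary efficacy set as all randomised subjects in their assigned arm, and count those with no post-baseline IGA as non-responders in the responder analyses. Keep dosed subjects with a baseline and at least one post-baseline IGA under the name evaluable set, for Part A efficacy and as a Part B sensitivity set. Other missing-data rules, such as those for subjects who withdraw after an early score, can sit in the SAP.

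**Section 14.4.** Delete the split by indication.

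**Section 8.3.** Limit identical-treatment replacement to Part A. State that any additional Part B subject takes the next number on the randomisation schedule and that withdrawn subjects stay in the analysis.

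**Cost.** Wording only; the 100:50 split is unchanged. Responder rates become slightly lower. Counting the unassessed as non-responders is a convention with its own possible error. If they would in truth respond at 30%, then at 10% v 5% loss the rates become 0.90 × 30% = 27.0% and 0.95 × 30% = 28.5%, a shift of −1.5 points. The evaluable-set analysis would show this.

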14.2 Demographics and Other Baseline Characteristics

Demographic and baseline characteristics will be summarized by dose using descriptive statistics (e.g., means/standard deviations, percentiles, frequencies).

14.3 Treatments

The number of subjects treated at each dose level will be summarized using descriptive statistics.

14.4 Safety Analysis

All treatment-emergent AEs will be summarized by dose group and indication (AD or PS). Counts and percents will be presented by treatment group for each observed system organ class (SOC) and preferred medical diagnosis.

The preferred terms and SOCs will be summarized in the following set of tables:

- All AEs;
- All AEs by maximum level of intensity;
- All AEs by closest relationship to the study medication.

Laboratory test variables will be summarized by dose group and study visit using descriptive statistics. Laboratory data collected from baseline and up to 7 days after a subject's last dose of study drug (or the date of the final follow up visit) will be included in the analysis.

Descriptive statistics will be used to summarize vital signs by dose group and study visit. Vital sign data collected from baseline and up to 7 days after a subject's last dose of study drug (or the date of the final follow up visit) will be included in the analysis.

14.5 Interim Analysis

No interim analysis is planned.

14.6 Determination of Sample Size

The sample sizes will provide sufficient data for clinical interpretation of safety and efficacy assessments. Sample sizes are not based on statistical considerations. The proposed enrollment

counts will provide validation of the safety objectives and a basis to estimate potential efficacy for future studies.

15 QUALITY CONTROL AND QUALITY ASSURANCE

15.1 Monitoring

BioMimetix JV, LLC, will monitor this study. The Principal Investigator at each clinical center should be available to the clinical trial monitor during monitoring visits and ensure that access to all documents and records is provided. The Principal Investigator agrees to cooperate with the clinical trial monitor to ensure that any problems detected in the course of these monitoring visits are resolved. All study documents must be made available upon request to the clinical trial monitor and other authorized regulatory authorities, including but not limited to the National Institute of Health and the FDA. Every reasonable effort will be made to maintain confidentiality during study monitoring.

15.2 Audits

The study may be audited by an audit team originating from the sponsor or its designee, or outside regulatory agencies. The investigator agrees to cooperate with the auditor to ensure than any problems detected in the course of the audit visits are resolved.

15.3 Data Management and Processing

15.3.1 Study Documentation

BioMimetix JV, LLC, will have access to the electronic database, with edit rights, for this clinical trial and will provide monitoring to confirm the accuracy of data entered into this database.

15.3.2 Case Report Forms

Data generated per protocol will be provided in paper or entered into an eCRF database provided by BioMimetix JV, LLC. When the CRFs have been completed, the clinical trial monitor will work with the study site coordinator or data management team to verify all source documentations and review data. Copies of the photographs will be filed as source documents and provided to the sponsor.

16 DATA MANAGEMENT PROCEDURES AND DATA VERIFICATION

The Principal Investigator at each clinical center is responsible for maintaining adequate records to enable the conduct of the study to be fully documented. Subsequent electronic review of the data may result in queries being generated that will be forwarded simultaneously to the investigator or designee for resolution. All data modifications resulting from review or querying of the data will be electronically tracked.

Any errors detected by either the monitor or the investigator should be communicated to the sponsor.

Copies of all regulatory documents such as the protocol, study approval letters, all CRFs, drug dispensing and accountability logs, all original patient consent forms, and all correspondence pertaining to the conduct of the study should be kept by the investigator for the maximum period of time permitted by local regulations.

16.1 Study Closure

Following completion of the study, the Principal Investigator at each clinical center will be responsible for ensuring the following activities for all subjects enrolled from his/her clinical center:

1. Data clarification and/or resolution of queries
2. Accounting, reconciliation, and destruction/return of used and unused study drugs
3. Review of site study records for completeness
4. Shipment of all remaining laboratory samples to the designated laboratories
5. Final report to the IRB

17 ADMINISTRATIVE AND ETHICAL CONSIDERATIONS

17.1 Regulatory and Ethical Compliance

This protocol was designed and will be conducted and reported in accordance with the International Conference on Harmonization (ICH) Harmonized Tripartite Guidelines for Good Clinical Practice, the Declaration of Helsinki, and applicable federal, state, and local regulations.

17.2 Institutional Review Board

The primary IRB for this study will be Western Institutional Review Board (WIRB). The protocol, informed consent form, advertising material, and additional protocol-related documents must be submitted to the IRB for review. The study may be initiated only after the Principal Investigator has received written and dated approval from the IRB.

All subsequent protocol amendments and changes to the informed consent form will be required to be approved by WIRB.

